8.0 Statistical analysis

Analyses described below represent planned analyses for primary and secondary measures. However, actual implementation of these analyses may differ slightly from what is described below, although the primary and secondary outcome measures will be as described.

Specific Aim 1: Localize neural effects of dIPFC iTBS

Primary outcome measures:

Primary outcome #1, BOLD activation: 2-back minus 1-back BOLD activation, voxelwise in FPN

Analysis Plan: MRI data analysis and strict quality control will use validated and established routines implemented in our laboratory. For processing BOLD images, we will use well-tested routines from FSL 5.0.1 and SPM12 for slice timing and realignment algorithms and spatial normalization (MNI-152) procedures implemented in VBM8. First-level analysis will use the general framework of the modified General Linear Model,(82) implemented in SPM12 with temporal convolution. For the *n-back* data the first-level design matrix will include regressors for 2-back and 1-back, iTBS/MRI session and 12 realignment parameters (including temporal derivatives of 6 realignment parameters). Second-level, between-subject analysis will consist of two-sided, one-sample t-tests for primary effects. For statistical inference across the FPN, and the entire brain, we will use topological false discovery rate (FDR)(83) providing corrected probabilities at $p<0.017$ ($0.05/3$, accounting for testing of 3 primary MRI measures). Given *a priori* hypotheses about FPN, a mask of activation (2-back minus 1-back, $p<0.001_{\text{uncorr}}$) at the group level, using all 4 MRI runs to provide the most representative mask, will be used as small volume correction.

(H1.1): iTBS to dlPFC, compared to vertex stimulation, will increase fMRI activation in the FPN during the n-back.

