any frame with FD > 0.5 mm from the regression analysis described below, yielding a scrub ratio for each subject. As it has been demonstrated that as many as 60% of frames can be removed and still yield analyzable results,(88, 89) we will use 60% deleted frames as a cutoff for analyzable subjects. Three-compartment segmentation of the high-resolution structural image from the VBM8 normalization will be applied to the functional time series to extract cerebral spinal volume (CSF) and white matter (WM) compartments, which will be subjected to a principal component analysis to identify the top 5 components in each,(90) which corresponds to heart rate and respiratory effects on the blood oxygenation level-dependent signal.(91) Adjusted time courses will be derived from sequential regressions of the time series with the following: Linear trend, 6 motion parameters, their temporal derivatives, the quadratics of these 12 parameters, 5 components from the PCA of CSF, 5 components of PCA of WM, followed by band pass filtering from 0.01 – 0.1 Hz, and then motion scrubbing. ICA-AROMA will be used to de-noise the data and remove additional, residual motion artifacts.(92) Global signal regression (GSR) will not be done because of concerns about non-uniform transformation of correlations introduced by GSR, problematic for group comparisons.(93) For the primary analysis, the time-course from a 6 mm radius sphere at the site of stimulation will be entered into the multiple regression and correlated with every other gray-matter voxel time-course in the brain for each subject. Correlation coefficients are Z-transformed and then entered into the second level, between-subject analyses as two-sided, paired t-tests to compare between sessions. Statistical inference will be controlled as above.

(H1.2) iTBS to dlPFC, compared to vertex stimulation, will increase FPN connectivity during resting state BOLD. Because TMS effects are observed away from the site of stimulation,(38-41) we are testing functionally-defined FPN networks. We recognize that the FPN defined by n-back will not be identical to the FPN defined by a dlPFC seed-based connectivity, although the two significantly overlap.

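### Sequential nuisance regressions, with no stated orthogonalisation, remove artefact incompletely from the resting-state connectivity outcome; one joint regression would avoid this

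*Combined protocol and SAP*

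**What the plan says.** The text is in section 8.0 Statistical analysis, Specific Aim 1, Primary outcome measure #2, Analysis Plan.

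- Method of nuisance removal: "Adjusted time courses will be derived from sequential regressions of the time series with the following".
- First regressors listed: "Linear trend, 6 motion parameters, their temporal derivatives, the quadratics of these 12 parameters".
- Remaining regressors and later steps, of which scrubbing is the last: "5 components from the PCA of CSF, 5 components of PCA of WM, followed by band pass filtering from 0.01 – 0.1 Hz, and then motion".
- A further step: "ICA-AROMA will be used to de-noise the data and remove additional, residual motion artifacts". Its place in the order is not given.
- Seed analysis: "the time-course from a 6 mm radius sphere at the site of stimulation will be entered into the multiple regression". The resulting correlations are Z-transformed and "entered into the second level, between-subject analyses as two-sided, paired t-tests to compare between sessions".
- Alpha is 0.017 (0.05/3), "accounting for testing of 3 primary MRI measures".

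Specific Aim 2 uses the same processing for H2.2 and changes only which sessions are compared. Neither aim says whether the six blocks are fitted together, or whether each block is first residualised on those before it.

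**The concern.** A least-squares residual is orthogonal to the regressors in that fit and to nothing else. If block two is correlated with block one and is fitted raw to the residual from block one, subtracting its fitted values puts a component along block one back into the series. Only a joint fit, or stepwise fitting with orthogonalised blocks, gives a residual orthogonal to all the regressors.

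Correlated blocks are likely here. The CSF and white-matter components are extracted from the functional time series, which the plan does not describe as already motion-cleaned. Scans are realigned to the 10th image, so slow head drift will tend to correlate with the linear trend and with its own square.

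What remains is common to the dlPFC seed and the voxels it is correlated with, so it appears as connectivity in a primary outcome. If its amount differed by condition, it would enter the H1.2 or H2.2 contrast as a false difference.

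**Working it through.** **No figure to reproduce.** The documents give no artefact size, no correlation between blocks and no power figure for this outcome. The one related number checks: 0.05/3 = 0.0167, rounded to 0.017.

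**Inputs from the documents**
- Regressors: 1 trend + 6 motion + 6 derivatives + 12 quadratics + 5 CSF + 5 white matter = 35.
- Frames: 10 minutes at TR 0.8 s = 600/0.8 = 750. The TR is stated for the n-back EPI (MRI Image acquisition) and assumed to apply to the resting scan.
- Subjects analysed: 40 (section 4.1).

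**Algebra for two regressors.** Let y = b1·x1 + b2·x2 + e, with x1 and x2 of unit variance and correlation r.
1. Regress on x1. The residual is b2(x2 − r·x1) + e.
2. Regress that on raw x2. The coefficient is b2(1 − r²). The artefact left is b2(x2 − r·x1) − b2(1 − r²)x2 = b2(r²·x2 − r·x1).
3. Its variance is b2²(r⁴ + r² − 2r⁴) = b2²·r²(1 − r²).
4. Its covariance with x1 is b2(r³ − r) = −b2·r(1 − r²), which is not zero unless r is 0 or ±1. Its covariance with x2 is b2(r² − r²) = 0.

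So the last regressor is fully cleared and the earlier one is not. A joint fit leaves none of the modelled artefact.

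| r | Artefact variance left, as a share of b2² |
|---|---|
| 0 | 0 |
| 0.1 | 0.01 × 0.99 = 1% |
| 0.3 | 0.09 × 0.91 = 8% |
| 0.5 | 0.25 × 0.75 = 19% |
| 0.7 | 0.49 × 0.51 = 25% |

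**Single-scan simulations.** These used the plan's blocks and a true seed-target correlation of zero. Block correlations and artefact amplitudes are assumptions. ICA-AROMA and scrubbing were not simulated.

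| Assumptions | Spurious r, sequential | Spurious r, joint |
|---|---|---|
| Component-motion r 0.2–0.6; shared amplitudes 0.5–1 neural SD; band-passed | 0.06 to 0.28 | −0.01 to 0.03 |
| Mixing weight 0–0.95; artefact variance equal to signal variance | 0.06 to 0.11 (0.06 to 0.09 after band-pass) | −0.005 to 0.004 |
| Random-walk motion referenced to frame 10; amplitude 0.7 neural SD; weight 0.2–0.6; band-passed | 0.09 to 0.12 | −0.005 to 0.014 |
| A further set, raw r 0.27–0.62 | 0.04 to 0.18 | not tabulated |

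In the second set raw r was about 0.50 and 6–10% of the shared artefact variance was left, so 90–94% was removed. Sequential fitting with each block orthogonalised to the earlier ones matched the joint fit. In the third set, a component-motion weight of zero still left r of 0.03.

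**Paired session contrast** (second set's model, weight 0.6, n = 40, alpha 0.017, 100 simulated trials per row, no true difference):

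| Artefact amplitude ratio between sessions | Mean z difference, sequential | Rejection, sequential | Rejection, joint |
|---|---|---|---|
| 1.0 | 0.001 | 1% | 1% |
| 1.25 | 0.04 | 25% | 1% |
| 1.5 | 0.09 | 89% | 0% |
| 2.0 | 0.20 | 100% | 3% |

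When amplitudes instead varied at random between sessions, unrelated to condition (0.5–1 neural SD, mixing 0.4, 60 trials), rejection was 1.7% under both methods. The SD of the paired z difference was 0.157 sequential against 0.153 joint, a ratio of 1.026.

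**The case against.** **The word may be loose.** The same Analysis Plan speaks of one regression, as in censoring "any frame with FD > 0.5 mm from the regression analysis described below, yielding a scrub ratio for each subject" and in the multiple regression for the seed, and section 8.0 allows implementation to differ slightly. This is a fair doubt about what will be run. But the multiple-regression phrase concerns entering the seed, and an analyst who follows the nuisance sentence as written would fit the blocks in turn.

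**The components might come from cleaned data.** If the CSF and white-matter components were taken from motion-residualised series, later steps could not put motion back; a simulation of that reading gave r of −0.01 to 0.02. The plan, however, describes extraction from the functional time series and mentions no prior cleaning.

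**Later steps may help.** ICA-AROMA is aimed at residual motion and could reduce what is left. Its position is unstated, and the plan does not assign it physiological signal. The simulated sizes therefore do not estimate the leftover for the full pipeline.

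**The test is a paired difference.** This stands. A reader might infer that the H1.2 and H2.2 contrasts are biased, but the documents do not show that. Order is counterbalanced, the scan protocol is identical across visits, and time of day and caffeine habits are to be kept consistent. Artefact could still differ by condition: stimulation site and concurrent task differ, subjects can tell the conditions apart (section 4.4), scalp pain is a listed risk (section 9.3.1.3), and the primary paired test has no motion covariate. That is a possibility only.

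**Not every signal returns.** A reader might also infer that each later step restores whatever was removed, or that white-matter signal is left in. Neither follows. Restoration needs correlated, non-orthogonalised blocks, and the regression residual is exactly orthogonal to the white-matter components because they come last.

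**Conclusion.** The point holds as a defect in the stated method. Fitted literally in sequence to correlated blocks, the plan's nuisance removal is incomplete, and the leftover is shared by seed and targets in primary outcome #2. The direction rests on algebra, given correlated blocks and no orthogonalisation. Correlation is likely for motion, drift and the CSF and white-matter components; on orthogonalisation the plan is silent.

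The size cannot be computed from the documents. The simulated range, roughly 0.04 to 0.28 for single-scan spurious r against about 0 (−0.01 to 0.03) for a joint fit, depends on assumed inputs and omits ICA-AROMA and scrubbing. Most artefact is still removed. The false-rejection rates of 25% to 100% show how sensitive the paired test would be to a condition-linked difference in artefact; they do not predict that one will occur. With equal artefact in both sessions there was no bias.

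The change is worth making because the joint fit is better under the literal reading, no worse under the others, and costs almost nothing.

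**What to change.** In section 8.0, Primary outcome measure #2, replace the sequential regressions with one simultaneous multiple regression per scan containing all 35 nuisance regressors and an intercept. Alternatively, state that each block is orthogonalised to all earlier blocks before it is fitted, which gives the same residuals. Use those residuals for all connectivity measures under both aims, and state where ICA-AROMA falls in the order.

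The cost is one SAP sentence and one script change. It needs no new data and loses no subjects.

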After localizer scans, subjects will undergo 3 scans: 1) BOLD-weighted fMRI (EPI, TR=800 ms, FOV=23, slice=2.4mm, 96x96 matrix) for the n-back task (8 minutes); 2) BOLD-weighted resting state scan for 10 minutes to obtain data for functional connectivity analyses (eyes open, looking at fixation cross); 3) pseudo-continuous ASL (pCASL) sequence following the recommendations of the ISMRM consensus(75). Our pCASL implementation will use a 3D stack of spirals acquisition(76) with 6 interleaves (TR=5000 ms, TE=4 ms, BW=125kHz, FOV=22 cm) preceded by a 1800 ms labeling period and an 1800 ms delay to allow the label spins to clear the arteries and enter the capillary/tissue compartment. Two hyperbolic secant inversion pulses at 600 and 1300 ms after labeling will suppress background signals, after first 2 frames to permit collection of spin density images for quantification. We will acquire 20 pCASL control-label image pairs, which will be reconstructed to a 128x128 matrix. Since the excitatory effects of iTBS have been demonstrated to last up to 60 minutes,(30) data acquisitions will occur in the appropriate time frame to capture iTBS effects. The last scan in the sequence will be a high-resolution structural scan (SPGR) for image normalization, as well as a T1 scan in the same prescription as the BOLD scans to facilitate normalization.

The scans and acquisition parameters described here are representative of what will be employed, although the actual acquisitions may differ slightly. Power-monitoring software on the scanner will ensure total energy delivered to the subject will remain within FDA guidelines. Specifically, the specific absorption rate (SAR) will be not greater than: 1) 4 W/kg averaged over the whole body for any period of 15 minutes; 2) 3 W/kg averaged over the head for any period of 10 minutes; 3) 8 W/kg in any gram of tissue in the head or torso; 4) 12 W/kg in any gram of tissue in the extremities, for any period of 5 minutes.

6.2.3 Visit 2 TMS session: This session will follow the MRI session for visit 2.

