Analysis Plan: Data processing of fMRI BOLD resting scans will begin with standard pre-processing steps. All scans will be slice-time corrected and realigned (FSL 5.0.9) to the 10th image acquired during a scanning session.(87) Subsequent processing will be performed with the Statistical Parametric Mapping SPM8 package (R4667; Wellcome Institute of Cognitive Neurology, London). Anatomic segmentation will be performed with the VBM8 toolbox in SPM8, using the high resolution SPGR T1 image, subsequently normalized to an MNI template using DARTEL. Normalizing warps to the MNI152 template are applied to the co-registered functional volumes, which are re-sliced and smoothed with an 8 mm isotropic Gaussian smoothing kernel. To assess and manage movement, we will calculate the frame-wise displacement (FD (88)) from the translation and rotation parameters from the realignment file, which is the sum (in millimeters) of the absolute values of frame displacement, i.e. successive 3D volumes, for all 6 parameters of rotation and translation. Rotational displacements are converted from degrees to millimeters moved on the surface of a 50 mm sphere. We use a 'scrubbing routine' to censor

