To examine state-dependency and modulation of iTBS effects by task, we will contrast MRI measures following iTBS applied to the dlPFC while subjects perform the n-back with MRI measures following iTBS compared to when they are in an unconstrained, resting state. The general analysis plan will use the same work-up of the imaging data as described above, the only difference being the MRI sessions that are compared with each other. Although directions of change are difficult to predict, we are predicting increasing activity as has been reported for iTBS applied during a deep encoding memory paradigm and not observed during shallow-encoding.(106) However, it is possible that cortex may become more efficient and less activation may be seen. The following primary hypotheses will be tested:

Primary outcome #1, BOLD activation: 2-back minus 1-back BOLD activation, voxelwise in FPN
(H2.1) For dlPFC stimulation during performance of a n-back task, compared to dlPFC
stimulation in a resting, unconstrained mental state, FPN activation to the n-back task will be
greater. For this analysis, the region of interest will be the FPN taken from the activation mask,
as described above. For a secondary measure to test H2.1, we will examine whole brain
activation, since change may occur outside this region of interest.

Primary outcome measure #2, BOLD connectivity: FPN connectivity to dlPFC iTBS stimulation
target

(H2.2) For dlPFC stimulation during performance of a n-back task, compared to dlPFC
stimulation in a resting, unconstrained mental state, connectivity with the dlPFC site of
stimulation will increase. For this analysis, the region of primary interest will be connectivity to
site of stimulation.

Primary outcome measure #3, rCBF at stimulation target

(H2.3) For dlPFC stimulation during performance of a n-back task, compared to dlPFC
stimulation in a resting, unconstrained mental state, resting perfusion at stimulation site will
increase. The primary region of interest will be the site of stimulation, and secondary analyses
will focus on the FPN, defined by n-back activation.

Specific Aim 3: Demonstrate improvement in cognitive control with iTBS, modulated by cognitive task during stimulation

Primary outcome measure: accuracy to 2-back

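### As listed, the resting-state pipeline band-pass filters before it removes high-motion frames and states no interpolation, so a motion spike that survives de-noising can leak into frames kept for primary outcome #2; the likely effect is small.

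*Combined protocol and SAP*

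**What the plan says.** The analysis plan for primary outcome measure #2 (Section 8.0, Specific Aim 1) defines framewise displacement (FD) as the "sum (in millimeters) of the absolute values of frame displacement, i.e. successive 3D volumes" over six motion parameters. A scrubbing routine censors "any frame with FD > 0.5 mm from the regression analysis described below, yielding a scrub ratio for each subject". On retention, "we will use 60% deleted frames as a cutoff for analyzable subjects".

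The time series is then regressed on a linear trend, 24 motion terms and ten CSF and white-matter components, "followed by band pass filtering from 0.01 – 0.1 Hz, and then motion scrubbing". The next sentence adds that "ICA-AROMA will be used to de-noise the data and remove additional, residual motion artifacts", without placing that step in the sequence. Interpolation or replacement of flagged frames is not mentioned anywhere.

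Seed-to-voxel correlations from this pipeline are Z-transformed and compared between sessions by two-sided paired t-tests, with no motion covariate named. Mean FD is a covariate only in the exploratory global brain connectivity (GBC) model. For Aim 2, "The general analysis plan will use the same work-up of the imaging data as described above", so H2.2 inherits the same steps. Section 8.0 opens by allowing that "actual implementation of these analyses may differ slightly from what is described below".

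The acquisition paragraph under Visit 2 specifies a "BOLD-weighted resting state scan for 10 minutes to obtain data for functional connectivity analyses". It gives a TR of 800 ms for the n-back run and no separate TR for rest.

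**The concern.** A 0.01-0.1 Hz filter turns a one-frame event into a ripple lasting many seconds. If flagged frames are still in the series when it is filtered, later deletion removes the centre of the ripple and leaves the rest. Residual spike signal shared by the seed and another voxel then raises their correlation, which is the quantity tested in H1.2 and H2.2. Because a subject may lose up to 60% of frames and still be analysed, runs with many flagged frames can enter the primary test.

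The plan already recognises that censoring interacts with frequency content: it drops scrubbing for the exploratory ALFF analysis for that reason. It does not take up the matter for the primary connectivity outcome.

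**Working it through.** The plan gives no figure for this point, so there is none to reproduce.

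**Inputs from the documents.** Band 0.01-0.1 Hz; 10-minute resting run; FD threshold 0.5 mm; 60% deletion limit; TR 0.8 s (n-back only, assumed for rest, with other values shown).

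**Inputs assumed.** Filter type (ideal FFT, or second-order Butterworth run forward and backward); residual spike size after all de-noising; share of frames flagged (5-20%); AR(1) noise with coefficient 0.6; identical residual spikes in seed and voxel.

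**Step 1: frames flagged per spike.** FD compares successive volumes, so a one-frame displacement flags two frames: the displaced one and the next.

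**Step 2: leakage, ideal filter.** A 600 s run has frequency spacing 1/600 Hz, so 0.01-0.1 Hz holds bins 6 to 60, which is 55 bins, or 110 with their conjugates. For a unit spike the filtered peak h0, which is also the in-band energy, is 110/N. If the next frame is a fraction q of the peak, the share of in-band energy left in kept frames is 1 - h0(1 + q²).

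- TR 0.8 s: N = 750, h0 = 0.147, q = 0.95, giving 1 - 0.147 × 1.90 = 0.72.
- TR 2.0 s: N = 300, h0 = 0.367, q = 0.73, giving 1 - 0.367 × 1.53 = 0.44.

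| TR (s) | Ideal | Butterworth |
|---|---|---|
| 0.8 | 72% | 62% |
| 1.0 | 66% | 55% |
| 1.5 | 53% | 42% |
| 2.0 | 44% | 34% |

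In-band energy is only part of the spike. As a share of raw spike energy, what remains is 0.147 × 0.72 = 11% (Butterworth 7.5%) at 0.8 s, and 0.367 × 0.44 = 16% (Butterworth 10%) at 2.0 s. At 0.8 s, 90% of the in-band energy spans ±12.0 s (ideal) or ±6.4 s (Butterworth); the two deleted frames cover 1.6 s.

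**Step 3: inflation within one session.** Simulated excess Fisher z for one seed-voxel pair with true r = 0, filter then delete, 5-20% flagged:

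- no residual spike: 0
- 0.5 SD: about 0.002-0.006
- 1 SD: about 0.006-0.03
- 2 SD: about 0.02-0.09

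A separate simulation with different spike assumptions (Butterworth) gave about 0.01-0.06 at 1 SD and 0.05-0.19 at 2 SD. The order of magnitude therefore depends on inputs the documents do not supply.

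**Step 4: the paired contrast.** Take a deliberately lopsided case at TR 0.8 s: every subject has 5% of frames flagged in one session and 20% in the other. The bias is 0.006 - 0.002 = 0.004 at 0.5 SD, 0.023 - 0.006 = 0.017 at 1 SD, and about 0.09 - 0.02 = 0.07 at 2 SD. The sampling SD of z for one pair in one run is about 0.10, so with 40 subjects the standard error of the mean difference is at least √2 × 0.10 / √40 = 0.022. The bias is about 0.2, 0.8 and 3 standard errors respectively, before real between-subject variation enlarges the denominator.

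**Step 5: added noise.** With 20% flagged, spikes add a per-pair SD of 0.009 (0.5 SD) or 0.018 (1 SD). Against 0.10 that is (0.09)² = 0.8% or (0.18)² = 3% more variance.

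**Step 6: interpolating first.** Mean excess z falls to about zero and the sampling SD stays near 0.10. Individual z values shift by an RMS of about 0.01-0.03 relative to the uninterpolated spike-free series.

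**Step 7: the retention limit.** At 60% deletion, 0.4 × 750 = 300 frames (4 minutes) remain.

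**The case against.** Four arguments against the point deserve weight.

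- **The order may not be what the list suggests.** The first regression described after the censoring sentence is the nuisance regression. If flagged frames are dropped from it or given their own regressors, the spike may never reach the filter. This stands as a real ambiguity. Placing scrubbing explicitly after the filter favours the direct reading but does not settle the matter.
- **De-noising may leave nothing to spread.** The plan uses 24 motion terms, ten tissue components and ICA-AROMA. If ICA-AROMA runs before the filter, the residual may be negligible. The simulations model none of these steps and give seed and voxel identical spikes, which is the worst case for correlation. This also stands; it is why residual size is an input and not a result.
- **Pairing cancels common inflation.** A reader might infer that H1.2 and H2.2 are biased towards a positive finding. The documents do not support that. Bias needs a between-session difference in residual motion, and none is shown. Head padding, mock-scanner practice, the same 600-pulse stimulation at each visit and counterbalanced order all make one less likely.
- **Interpolation has its own cost.** It does move individual z values, by about as much as a 0.5-1 SD spike does. In simulation, however, the shift had mean zero and did not increase total variance, so it does not defeat the fix. Exact removal holds only for spikes confined to flagged frames.

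**Conclusion.** The point holds as a minor one. The listed order is filter then scrub, interpolation is not stated, and spread into kept frames follows mathematically for any spike that reaches the filter. Between about a third and three quarters of in-band spike energy stays behind over the TRs and filters examined.

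The consequence for the primary contrasts is probably negligible if residual spikes are around 0.5 SD or less. It would matter only with large residuals (about 2 SD) together with a marked session difference in motion. Neither can be established from the documents, and no inflation of the false-positive rate is claimed. Nor should the long reach of the filter be taken to mean that most kept frames are contaminated: being near a spike says nothing about how much signal it leaves.

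Confidence is moderate. The mechanism is certain; the size rests on assumed residual spikes, an assumed resting TR and an unresolved sentence about where censoring applies.

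**What to change.** Replace the order in the primary outcome #2 plan with one explicit sequence:

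1. Compute FD and flag frames first.
2. Leave flagged frames out of the nuisance fit, and reconcile the censoring sentence with this.
3. Interpolate them before the band-pass, or fit regression and filtering together in one censoring-aware model.
4. Delete them before correlating.

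Place ICA-AROMA before the filter, or at least state its position. Use the same sequence for H2.2 and the GBC analysis, and state the resting TR. Report mean FD and the share of flagged frames by session, so a reader can see whether motion differed between the compared conditions. A sensitivity analysis on the session difference in mean FD is optional.

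The cost is a small script change and a few sentences in the plan, with no new data and no change of outcome. The Section 8.0 allowance for slight differences in implementation leaves room for it but does not specify it. The one downside is the small, mean-zero shift in individual z values from interpolation.

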7.1.5 Quality assurance and quality control for data acquisition

Clinical assessments: Assessors will be trained on assessment instruments and established according to laboratory standards and good inter-rater reliability

MRI data: The fMRI lab maintains weekly schedule of calibration runs to assure consistent operation. Processing pipelines and standard operating procedures are in place ensure that data is processed in a uniform manner. Quality control at each step will be carried out by study staff to verify, through multiple metrics, image quality. Databases will track processing steps, in addition to automatically generated log files.

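### The plan names two different primary regions for rCBF (H1.3 and H2.3) and prints the stimulation-site sphere with a 6 cm radius; a motion check for connectivity is an optional extra

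*Combined protocol and SAP*

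**What the plan says.** **rCBF.** The combined protocol and SAP describes the region in five places.

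- Section 2.0 lists rCBF at the stimulation target as a primary outcome for Aims 1 and 2, and rCBF in the FPN as a secondary one.
- The heading of Primary outcome measure #3 in section 8.0 names the stimulation target.
- The analysis paragraph under that heading places the ROI analysis in the FPN mask from the n-back task, follows with a two-sided paired t-test at 0.017, and assigns a sphere of 6 cm radius at the stimulation site to the secondary analyses.
- H1.3, directly below, makes the site primary and the FPN secondary.
- H2.3 does the same for Aim 2. The Aim 2 introduction also carries over the Aim 1 work-up, "the only difference being the MRI sessions that are compared with each other", so the conflicting paragraph applies there too.

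**Connectivity.** Under Primary outcome measure #2 the plan states: "To assess and manage movement, we will calculate the frame-wise displacement". Frames above 0.5 mm are censored, "yielding a scrub ratio for each subject", and "we will use 60% deleted frames as a cutoff for analyzable subjects". Motion and tissue regressors are removed, and "ICA-AROMA will be used to de-noise the data and remove additional, residual motion artifacts". The Z-transformed correlations are then "entered into the second level, between-subject analyses as two-sided, paired t-tests to compare between sessions". Section 7.1.5 adds general quality control: "Quality control at each step will be carried out by study staff to verify, through multiple metrics, image quality". Mean FD is a second-level covariate only in the exploratory global brain connectivity ANCOVA (dlPFC versus vertex).

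**The concern.** Alpha is divided by three because there are three primary MRI measures. That division protects the conclusions only if each measure is one defined quantity. For rCBF an analyst following the analysis paragraph and one following the hypotheses would test different regions, and each could cite the plan. If the two results disagreed, the plan could not say which was confirmatory.

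The radius adds to this. It sits in the sentence that defines the site region, and a sphere of that size could not represent a stimulation site.

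For connectivity the issue is smaller. FD will exist for the resting scans, but the plan does not say that it will be compared between the sessions contrasted in H1.2 or H2.2. A reader of a positive result would have the scan-level cleaning to rely on, but no direct evidence that residual motion was similar in the two conditions.

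**Working it through.** **1. Region, side by side**

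| Place | Primary | Secondary |
|---|---|---|
| Section 2.0 outcome list | Stimulation target | FPN |
| Section 8.0, heading of outcome #3 | Stimulation target | not stated |
| Section 8.0, analysis paragraph of outcome #3 | FPN mask (t-test at 0.017) | Site sphere; whole brain |
| Section 8.0, H1.3 | Stimulation site | FPN |
| Section 8.0, H2.3 | Stimulation site | FPN |

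Four places agree and one differs. The one that differs is the paragraph that an analyst would implement.

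**2. Alpha**

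The plan's figure: 0.05/3 = 0.0167, printed as 0.017. If either rCBF region may be called primary for one contrast, the chance that at least one rejects under the null is:

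- lower limit (the two tests always agree): 0.017;
- independent tests: 1 − (1 − 0.017)² = 1 − 0.9663 = 0.034;
- upper bound: 2 × 0.017 = 0.034.

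The documents give no correlation between the regions, so the range is 1.7% to 3.4% for each of H1.3 and H2.3.

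**3. Sphere**

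Volume = (4/3)πr³, and (4/3)π × 6³ = 904.8.

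- r = 6 cm: 904.8 cm³, about 905 mL.
- r = 6 mm: 904.8 mm³, about 0.90 mL.

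The ratio is 10³ = 1,000. A 6 cm radius means a 12 cm diameter, and 12/22 = 55% of the 22 cm field of view given for the pCASL scan. The connectivity seed and the global brain connectivity analysis both use 6 mm at the same site.

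**4. Optional motion point: what it could be worth**

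The documents give no motion data, so these are single-test illustrations with n = 40 and two-sided alpha 0.05/3. They do not transfer directly to the voxelwise FDR search. Assumed quantities: r, the correlation between the session differences in mean FD and in connectivity, and the mean motion shift in SD units. The standardised bias is r × shift. Type I error of the planned paired t-test (noncentral t, 39 df), against 1.7% nominal:

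| r | Shift 0.3 SD | Shift 0.5 SD |
|---|---|---|
| 0.1 | 1.8% | 2.2% |
| 0.2 | 2.4% | 3.9% |
| 0.3 | 3.4% | 7.0% |

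Power at an assumed standardised effect of 0.40, with r = 0.1 and the same shift for both analyses:

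| Shift | Planned, bias with the effect | Planned, bias against the effect | Adjusted for the FD difference |
|---|---|---|---|
| 0.3 SD | 59% | 44% | 47% |
| 0.5 SD | 64% | 40% | 41% |

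So adjustment may lower or slightly raise power, depending on the direction of the bias.

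Precision of a by-condition motion table: the 95% half-width is t(0.975, 39)/√40 = 2.023/6.325 = 0.32 SD. A test at two-sided 0.05 would detect a 0.5 SD shift with 87% power and a 0.3 SD shift with 46%.

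Retained data: the 800 ms TR is printed with the n-back scan ("BOLD-weighted fMRI (EPI, TR=800 ms"). If it also holds at rest, 10 minutes is 600/0.8 = 750 frames. A 60% cutoff applied to each session can then leave 0.40 × 750 = 300 frames, or 240 s (4 minutes).

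**The case against.** **On rCBF.** Section 8.0 says that implementation may change slightly while the outcome measures stay as described. Since section 2.0 names the stimulation target, the intended region can be inferred, and 6 cm looks like a slip of units. Both points are fair, and they support the direction of the fix. They do not remove the conflict, because the paragraph carrying the 0.017 test still describes a different region.

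A reader might infer that the region was left open on purpose, or that the error rate is already inflated. The documents support neither. Inflation arises only if the choice follows the results.

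**On motion.** Most of this objection stands.

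- Each resting scan is cleaned with 24 motion terms, 10 CSF and white-matter components, censoring and ICA-AROMA.
- Pairing removes stable differences between people, and session order is counterbalanced.
- Mean FD already enters a second-level model on the same scans, although for an exploratory outcome, for dlPFC versus vertex only, and without saying whether it is a value per subject or per session.
- The one plausible route is discomfort that differs by site. It concerns H1.2 only and is weakened by the tolerability run, by the coil adjustments for pain, and by the n-back scan listed before the resting scan.
- Both H2.2 conditions stimulate the same target with the same pulse pattern, and the documents suggest no route for a motion difference.

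A reader might infer that the connectivity result is confounded by motion. Nothing in the documents shows that motion differs by condition. A reader might also infer that the 60% cutoff pools sessions, leaving one session with no minimum. The text never mentions pooling; it only fails to say that the cutoff is per session.

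**Conclusion.** The rCBF contradiction is established from the text alone and needs no assumption. One of the three alpha-split measures has two candidate primary regions, in both Aim 1 and Aim 2. If the choice were made after seeing results, the error for each contrast would lie between 1.7% and 3.4% instead of 1.7%. The printed radius is 10 times, and its volume 1,000 times, that of the 6 mm sphere used elsewhere at the same site.

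The motion point is an optional improvement to reporting and not a defect in the primary test. Its possible size (type I error of 1.8% to 7.0% in the single-test illustration) rests wholly on assumed correlations and shifts.

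**What to change.** **Needed, before any condition contrast is analysed.**

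- Rewrite the analysis paragraph of Primary outcome measure #3 so that the paired t-test at p < 0.017 for H1.3 and H2.3 is on the stimulation-site sphere, with the FPN mask secondary. This matches section 2.0, the outcome heading and both hypotheses.
- Correct the radius to agree with the 6 mm sphere used elsewhere in section 8.0.

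The cost is wording only.

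**Optional, for H1.2, and for H2.2 only for completeness.**

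- Keep the planned paired t-test as primary.
- Report mean FD and minutes retained by condition, with the paired difference and its 95% CI. At n = 40 a p-value alone would miss a 0.3 SD shift more often than not.
- State that the 60% cutoff applies to each session, and whether mean FD covers all frames or only those retained.
- Prespecify one sensitivity model: session-difference connectivity images with the uncentred session difference in mean FD as covariate, using the same mask and FDR.

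This costs one table and one second-level model, and no new data. The model uses one degree of freedom. Its covariate is measured after stimulation, so it estimates the effect at equal motion and should not replace the primary test. It does not correct for unequal precision when retained minutes differ.
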